### **8.3 Clinical Assessments and Procedures during the Double-blind Treatment Period**

Patients will visit the clinic each week for the first 8 weeks and every 2 weeks thereafter until the end of the treatment period (week 48) as described in Appendix A. At each visit, the patient will receive an infusion and will be checked for:

- Adverse events
- Previous and concomitant medications

Complete assessments as described for visit 2 (see *Section 8.2* above) will be performed 4 weeks and 8 weeks after randomization (at visit 6 and visit 10). Thereafter, patients will have complete assessments every 8 weeks until the end of the week 48 treatment period (at week 16, 24, 32, 40 and 48). Unless otherwise specified, blood and urine specimens will be collected prior to study drug dosing.

Markers of inflammation, oxidation, lipid metabolism and CV risk (See *Section 8.10*) will be assessed at baseline, week 8, week 24 and week 48 (end of treatment).

HbA1c assessment will be performed only at baseline (See *Appendix A*).

Anti-ApoA-1 antibody assessment will be performed at week 8, week 24 and week 48 (end of treatment).

Blood samples will be collected for biomarkers assessments at week 24.

A blood sample will also be drawn two hours after initiation of the infusion to assess the PK, at week 24.

Follow-up 3T-MRI will be done at the end of the induction treatment phase (week 8), week 24 and at the end of the overall week 48 treatment period.

Follow-up FDG-PET/CT will be performed only once 24 weeks after randomization.

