## 8.6 Specific Imaging Assessments

### 8.6.1 Assessment of Vascular Structure of the Carotid and Femoral with 3T-MRI

Patients will have 3T-MRI imaging performed at Baseline, Week 8, Week 24, Week 48 and Week 72 (optional) for carotid and femoral Mean Vessel Wall Area (MVWA) and carotid normalized wall index (NVWI) measurements.

The baseline 3T-MRI can be done anytime during the screening period, before the randomization provided all other selection criteria are satisfied.

All images will be collected for their review by an imaging expert, with a window of +/- 7 days around the strict date.

The detailed procedure for performing and collecting of 3T-MRI images will be outlined in the Imaging Manual.

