#### **8.6.2 Assessment of target (plaque) background (blood) ratio with PET/CT**

Patients will have two PET/CT scans with labelled glucose  $^{18}\text{F}$ -deoxyglucose at Baseline and Week 24 only at the sites appropriately equipped.

The baseline PET/CT scan can be done anytime during the screening period, before the randomization.

All images will be collected for their review by an expert, with a window of +/- 7 days around the strict date.

The detailed procedure for performing and collecting PET/CT scans will be outlined in the Imaging Manual.

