6.1 Analysis populations of patients

The statistical analysis will be based on the three populations defined below. To be part of a population, patients should have signed informed consent and fullfill all inclusion / exclusion criteria. Some criteria have been added after the start of the study. Hence patients included before will be considered as compliant to these criteria via a Not Applicable (NA) status.

Safety population

The safety population will comprise all randomized patients who received at least one dose of study medication.

Safety analysis will be performed on the safety population according to the actual treatment received.

Modified Intent-To-Treat (mITT) population

The mITT population will comprise all randomized patients for whom at least one of the following conditions is satisfied:

- 3T-MRI assessment available at baseline (W0) and at least one post-baseline 3T-MRI assessment available
- 18FDG-PET/CT assessment available at baseline (W0) and at least one post-baseline 18FDG-PET/CT assessment available

Per Protocol (PP) population

The PP population will comprise all patients of the mITT population without any major protocol deviations (*Cf.* section 6.3).

Defining study populations and excluding patients from the analysis will be a joint decision taken by Sponsor and ICTA PM' representatives (Statistician and Project Leader). Patients to be excluded and

CER-001-CLIN-009 CER-001

reasons for their exclusion will be discussed during data review meetings, before database lock and unblinding.

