7.4.1.2 Supportive analysis

As a supportive analysis, the linear mixed model described in the previous section (7.4.1.1) will also be fitted to observed and imputed data for the mITT population. Thus, a multiple imputation procedure will be set up and is described below.

First, in case of non-monotone missing data pattern, a MI procedure will be applied using a MCMC algorithm to create 20 imputed datasets with a monotone missing data pattern. The number of burnin iterations before each imputation will be set to 200. Sample SAS code is displayed below.

Sample SAS Code

```
proc mi data=DATWIDE nimpute=20 seed=111 out=MONODAT;

var TRTGRP GENETIC_MUT BASELINE CHANGE8 CHANGE24 CHANGE48;

mcmc chain=MULTIPLE impute=MONOTONE nbiter=200;

run;
```

Second, the 20 datasets with a monotone missing data pattern will be fully imputed based on a monotone method. Corresponding sample SAS code is provided below.

Sample SAS Code

```
proc mi data= MONODAT nimpute=1 seed=222 out=MONODAT;

by _IMPUTATION_;

class TRTGRP GENETIC_MUT;

var TRTGRP GENETIC_MUT BASELINE CHANGE8 CHANGE24 CHANGE48;

monotone regression (CHANGE8 CHANGE24 CHANGE48);

run;
```

Finally, the linear mixed model described in section 7.4.1.1 will be applied for each complete data sets producing 20 analysis results. The final treatment effect estimate will be obtained combining these 20 estimates as follows:

CER-001-CLIN-009 CER-001

Sample SAS Code

```
proc mianalyze data=MRESULTS_;

modeleffects ESTIMATE;

stderr STDERR;

ods output parameterestimates=RESULTS_;

run;
```

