7.4.1.3 Sensitivity analyses

7.4.1.3.1 Missing Not At Random data mechanism

These sensitivity analyses require partitioning the analysis mITT population into groups, based on treatment group and available information about the reasons for missing values, before multiple imputation.

Control-based I: all dropouts grouped with placebo

In the first control-based sensitivity analysis, all monotone missing values will be imputed such as all dropouts and the placebo group form a subset with similar trajectories. A dataset, MONOREF_all, containing all the placebo group subjects and the treatment group subjects with missing data, will be imputed as shown in sample SAS code below. The complement of MONOREF_all will be the complete observation treated group data, so this could be concatenated with the 20 imputed datasets in DATIMP1.

Sample SAS Code

```
proc mi data= MONOREF_all nimpute=1 seed=333 out=DATIMP1;
by _IMPUTATION_;
class GENETIC_MUT;
var GENETIC_MUT BASE CHANGE8 CHANGE24 CHANGE48;
monotone regression (CHANGE8 CHANGE24 CHANGE48);
run;
```

Control-based II (informative-dropout): poor-outcome dropouts grouped with placebo

In the informative-dropout sensitivity analysis, some subjects are characterized as likely to have poor unobserved outcomes, for example if study withdrawal is due to clinical worsening. In this case, the datasets in MONODAT (monotone dataset) will be first split by treatment groups, either randomized to the experimental (TRTGRP) or reference/placebo (REF) condition, and then the poor-outcome dropouts will be shifted to the REF group, resulting in the datasets MONOTRT_minus and MONOREF_plus. The multiple imputation will be conducted separately for each subset as shown in the following sample code. The output datasets, DATIMP2T and DATIMP2R, will simply be concatenated before the analysis step.

```
proc MI data= MONOTRT_minus nimpute=1 seed=444 out=DATIMP2T;
by _IMPUTATION_;
class GENETIC_MUT;
var GENETIC_MUT BASE CHANGE8 CHANGE24 CHANGE48;
monotone regression (CHANGE8 CHANGE24 CHANGE48);
run;

proc MI data= MONOREF_plus nimpute=1 seed=555 out=DATIMP2R;
by _IMPUTATION_;
class GENETIC_MUT;
var GENETIC_MUT BASE CHANGE8 CHANGE24 CHANGE48;
monotone regression (CHANGE8 CHANGE24 CHANGE48);
run;
```

Control-based III: poor-outcome dropouts act like reference

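### mITT entry does not require a carotid change, yet the carotid imputation analyses run on the whole mITT, and Control-based I can impute CER-001 patients who were still attending as if they were placebo-like dropouts

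*SAP*

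**What the plan says.** SAP 6.1 defines one mITT set for all efficacy endpoints: "The mITT population will comprise all randomized patients for whom at least one of the following conditions is satisfied". The conditions are "3T-MRI assessment available at baseline (W0) and at least one post-baseline 3T-MRI assessment available" and "18FDG-PET/CT assessment available at baseline (W0) and at least one post-baseline 18FDG-PET/CT assessment available". The first names no artery, although Protocol 8.6.1 schedules the MRI "for carotid and femoral Mean Vessel Wall Area (MVWA) and carotid normalized wall index (NVWI) measurements".

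The main analysis (SAP 7.4.1.1) is an MMRM on observed carotid changes without imputation. In the supportive analysis (7.4.1.2), "the linear mixed model described in the previous section (7.4.1.1) will also be fitted to observed and imputed data for the mITT population". Its sample code lists the baseline and the three carotid changes, and nothing restricts it to patients who have a carotid value.

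Control-based I (7.4.1.3.1) is introduced as grouping dropouts with placebo. The dataset it builds is described differently, as "containing all the placebo group subjects and the treatment group subjects with missing data". The imputation model for that dataset has no treatment term.

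Follow-up PET/CT "will be performed only once 24 weeks after randomization" (Protocol 8.3), and PET/CT is done at "Baseline and Week 24 only at the sites appropriately equipped" (Protocol 8.6.2). After early stopping of study drug, Protocol 8.7 adds an MRI but mentions no PET/CT.

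**The concern.** The PET/CT condition can only add patients who fail the MRI condition, that is, patients with no MRI pair and hence no carotid change. The unnamed artery leaves a second route: a usable femoral pair with a missing or unreadable carotid. Such patients contribute nothing to the MMRM but receive a full set of imputed carotid changes in the supportive and control-based analyses. The main and sensitivity analyses then rest on different patients under one label.

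Control-based I is there to show whether dropout could explain the result. As coded, it also gives placebo-like outcomes to CER-001 patients whose only problem was a missing or unusable carotid scan. If it came out weaker than the main analysis, a reader could not tell whether dropout or image availability was the cause. With about 20 CER-001 patients, one or two are enough to matter.

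**Working it through.** **1. The plan's own figure.** Inputs from SAP section 3: 16 and 8 completers, difference 6.7, SD 4.5, two-sided alpha 0.05. Noncentrality = 6.7 / (4.5 × √(1/16 + 1/8)) = 6.7 / 1.949 = 3.44. With 22 degrees of freedom the power is 90.7%, which reproduces the stated 90%. Also 24 / 0.8 = 30 randomised, as planned.

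**2. Following one patient.** Take a CER-001 patient with a PET/CT pair and no carotid change.
- SAP 6.1: in mITT, through the PET/CT condition.
- 7.4.1.1: no observed change, so no contribution.
- 7.4.1.2, first step: only non-monotone gaps are filled. A patient missing all three changes already has a monotone pattern and passes through unfilled.
- 7.4.1.2, second step: all three changes are imputed, with treatment in the model.
- 7.4.1.3.1, Control-based I: the patient has missing data, so joins the placebo set and is imputed without a treatment term.
- Protocol 8.3, 8.6.2 and 8.7: the only scheduled post-baseline PET/CT is at Week 24 and none is added at early stopping, so the patient was still attending around Week 24.

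**3. Size in Control-based I.** Let k be the number of such CER-001 patients and d the number of true CER-001 dropouts, with 20 randomised to CER-001. Only 20 − d − k patients carry the drug effect.
- Expected effect as written: 6.7 × (20 − d − k) / 20.
- Expected effect with the k patients left out: 6.7 × (20 − d − k) / (20 − k).

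Leaving them out is the right comparator, because no wording of the SAP can supply their missing scans. The last two columns come from a simulation at the planning values: 20:10 randomised, 2 placebo dropouts, Week 24 only, missing CER-001 values drawn from the placebo model, 20 imputations, Rubin pooling.

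| d | k | Effect as written | Effect, k left out | Significant as written | Significant, k left out |
|---|---|---|---|---|---|
| 2 | 1 | 5.70 | 5.99 | 82% | 86% |
| 2 | 2 | 5.36 | 5.96 | 75% | 85% |
| 4 | 1 | 5.03 | 5.29 | 65% | 73% |
| 4 | 2 | 4.69 | 5.21 | 56% | 70% |

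The loss due to the rule is 4, 10, 8 and 14 percentage points. Four CER-001 and two placebo dropouts correspond to the plan's 20% discontinuation; two CER-001 dropouts is a milder case. Pooling with small-sample degrees of freedom lowers all the percentages but leaves the losses about the same.

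**4. Size in the other analyses.** A second simulation used 16:8 patients, three visits, an assumed between-visit correlation of 0.5, and no other missing data. Each cell gives the mean effect and the power at Week 24.

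| k | Observed data | Imputation under MAR | Control-based I |
|---|---|---|---|
| 1 | 6.73, 91% | 6.71, 90% | 6.27, 84% |
| 2 | 6.66, 89% | 6.60, 88% | 5.83, 74% |
| 4 | 6.78, 87% | 6.62, 84% | 5.00, 43% |

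MAR imputation adds noise with almost no bias. The material effect is in Control-based I.

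**The case against.** The strongest reply is that nothing carrying the trial's decision changes. The primary MMRM and the secondary models use observed data. No success rule is attached to Control-based I, and its error works against the drug. This stands, and it limits the weight of the point.

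The second reply is rarity. Contraindication to MRI is an exclusion, MRI is scheduled at three follow-up visits and again after early stopping, one session covers both arteries, and PET/CT is limited to equipped sites. This also stands: k = 0 is plausible.

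The third reply is that population membership is settled at data review before lock, that SAP 6.3 reports the numbers in each set, and that Protocol 12.5 also uses one mITT set. This stands only in part. The SAP gives the review meeting no endpoint-specific rule to apply, the results template (Table 7) shows no N, and the protocol plans no imputation.

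The documents do not support several stronger readings that a reader might infer:
- **That the primary estimate is biased.** It is not; these patients add nothing to it.
- **That the loss should be measured against a trial with complete carotid scans.** That gives about 86 to 87% significance with two dropouts and 74 to 76% with four, but it charges the SAP with data that no rewording can recover.
- **That every such patient was still attending.** This is certain for PET-only entrants. Someone who enters on a Week 8 femoral scan may be a true dropout.
- **That Control-based II and III misclassify them too.** Those analyses move only poor-outcome dropouts, although they still impute these patients' carotid changes.
- **That a missing carotid baseline will be imputed.** The baseline is in the variable list, but the imputation statements name only the changes and the prose is silent. The point does not depend on it.

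**Conclusion.** The point holds, with limited reach. mITT entry does not ensure a carotid change, imputation is not restricted to patients who have one, and the Control-based I dataset does not match its own description. The main analysis is untouched, the MAR imputation is nearly unbiased, and the Control-based I error is conservative. If one or two such CER-001 patients exist, the rule costs Control-based I about 4 to 10 percentage points of significance with two CER-001 dropouts, and 8 to 14 with four.

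These figures rest on assumptions: the count of such patients, the dropout numbers, and a simplified model at Week 24 only, without baseline, mutation or interaction terms and without true dropouts' Week 8 values. They are also on the percent-change scale of the sample size section, whereas the endpoint is analysed in mm². The point should be corrected before lock because the change is cheap and Control-based I would otherwise be hard to interpret. It gives no reason to doubt the primary analysis.

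**What to change.** - In SAP 6.1 (or 7.4.1), define the carotid analysis set as mITT patients with a baseline and at least one post-baseline carotid MVWA. Use it for the MMRM and for every imputation analysis. Requiring a carotid baseline alone would not be enough, because patients with no carotid change would still be imputed.
- Define the femoral set in the same way, and use the PET/CT condition for TBR only.
- In 7.4.1.3.1, build the Control-based I dataset from placebo patients plus CER-001 patients who stopped study drug or left the study. Impute other missing CER-001 values under MAR within their own arm.
- Report the N analysed for each endpoint, including in the Table 7 template.

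The cost is a few sentences and a small code change before database lock. The carotid N may be slightly below the mITT N, and Control-based I becomes slightly less conservative.

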6.2 Protocol deviations

A list of protocol deviations has been written by ICTA PM and sent to the sponsor for approval. The list contains possible protocol deviations (according to inclusion/exclusion criteria, disallowed treatments, minimum treatment exposure, and calendar of visits...), and significant deviations which require immediate information to the Sponsor. This list may be updated in the course of the data management process, and will be finalized during the data review meetings before database lock and unblinding.

TANGO_DeviationsLi

During the data review, the impact of each deviation (minor/major) on the primary endpoint will be discussed and thus, the list of patients to be excluded from the PP population will be defined.

Number and percentage of patients with at least one deviation, at least one major deviation, at least one deviation by type (Entry criteria / Study procedures / Investigational medicinal product) will be described. Each deviation will also be summarized by the number and percentage of patients who experienced it.

6.3 Disposition of patients

The following data will be described:

- Number of screened patients [a]
- Number of screening failures and reasons for screening failures
- Number of randomized patients grouped by treatment
- Number of patients for whom the blind was broken
- Number of patients with ABCA-1, ApoA-1 or both mutations
- Number of patients who did not receive any medication and reason for non-treatment
- Number of patients who received double-blind medication
- Treatment actually received (CER-001/Placebo)
- Number of patients who completed the study
- Number of premature discontinuations of the study treatment and reason for premature discontinuation (at each visit, and overall)
- Number of premature withdrawals and reason for premature withdrawal (at each visit, and overall)
- Number of patients who completed the induction period grouped by treatment (visit at W8 performed)
- Number of patients who completed the maintenance period grouped by treatment (visit at W24 performed)
- Number of patients who completed the extension period grouped by treatment (visit at W48 performed)
- Patient's follow-up duration
- Inclusion date of the first patient (FPFV: First Patient First Visit), date of first visit of the last patient (LPFV) and last visit date of the last patient (LPLV: Last Patient Last Visit)
- Number of patients in each analysis set and reasons for exclusion from the analysis sets
- Number of visits performed

CER-001-CLIN-009 CER-001

- Flow chart for analysis populations
- Flow chart for disposition of patients
- Flow chart for visits

[a] A screened patient is a patient who completed a screening visit

7. Statistical methodology

7.1 General principles

7.1.1 Software

All statistical analyses will be performed using Statistical Analysis System (SAS®) release 9.4. All computer programs will be developed and validated according to ICTA PM (CRO) standard operating procedures (SOP).

7.1.2 Descriptive statistics

Quantitative data will be summarized by the following descriptive statistics: number of data available, number of missing data, mean, standard deviation, first quartile (Q1), median, third quartile (Q3), minimum and maximum. If relevant, a 95% t-based mean confidence interval (CI) will also be presented.

Qualitative data will be summarized by the following descriptive statistics: number of data available, number of missing data, frequency and percentage for each modality.

Percentages will be calculated without taking into account missing data.

7.1.3 General statistical tests

No general statistical tests are planned. Statistical tests will be performed when running analysis of covariance (ANCOVA) and are detailed in section 7.5.

7.1.4 Management of missing or incomplete data

Previous and concomitant medications

For the purposes of determining whether a medication was taken during the conduct of the study, any missing or partial start or stop dates for which a definitive determination cannot be made will result in that medication will be assumed to be concomitant, to be conservative.

Linear Mixed Model

Missing data handling for assessing efficacy endpoints using linear mixed model will be described in section 7.4.1.

Adverse Events (AE)

If part of the date/time of an AE is missing, but the existing parts allow determination of timing of AE onset/end relative to start and stop date of the study drug, then the AE will be classified (treatment-emergent or not treatment-emergent) per review of the existing parts of the date/time field. If timing of the AE onset/end relative to start and stop date of the study medication cannot be made, then the AE will be assumed to be a Treatment-Emergent Adverse Event (TEAE).

Vital signs, physical examination, ECG and laboratory values

For absolute, relative changes and shifts from baseline (W0), in case of missing data for the baseline value, the latter will be replaced by the value obtained at screening visit.

CER-001-CLIN-009 CER-001

7.1.5 Handling of dropouts

Dropouts will be handled for the primary endpoint as described in section 7.1.4.

The reasons of study termination will be assessed among treatment groups as well as the proportion of dropouts at each visit performed (*Cf.* section 6.4).

7.1.6 Handling of study centre effects

No centre effect will be assessed.

7.1.7 Presentation of results

Statistical Tables, Figures and Listing (TFL) will be produced in English, and templates are shown in appendix 12.2.

For summary statistics, mean, standard deviation and median will be presented with 1 more decimal place than the raw data; min and max with the same number of decimal places as the raw data. P-values will be presented with three decimal places.

7.1.8 Examination of subgroups

Individual genetic mutation will compose the three following subgroups:

- ABCA-1
- ApoA-1
- ABCA-1 & ApoA-1

These subgroups will be used as independent variable for each primary and secondary ANCOVA. Description of each exploratory outcome will also be performed on these subgroups.

7.1.9 Validation levels

Internal review by the statistician in charge of the project will be performed, including SAS® codes and programming, SAS® logs and outputs and edition of the TFL. Then, an external review of the TFL will be performed by the ICTA PM project manager and by the sponsor.

A double-programming of the primary endpoint analysis will be performed.

7.2 Demographic and other baseline characteristics

Demographic and other baseline characteristics will be described according to randomization group for all randomized patients. Description will also be performed for each subgroup of interest (based on genetic mutation). Baseline is defined as the last observation for any given parameter observed prior to the first infusion of study drug.

The following characteristics will be summarized using standard descriptive statistics (Cf. 7.1.2):

